9.6.8 Timing of Dose for Each Subject

In **Part 1** doses will be administered on day 1 at approximately 9.00 a.m.

In **Part 2** doses will be administered on Day 1 at approximately 9.00 am. For doses taken at home, patients should be advised to administer the study drug at approximately the same time as the first dose, each day it is taken.

9.6.9 Blinding

A designated individual from the Pharmacy Department at Simbec will generate the randomisation code under the guidance of a statistician. All site and Sponsor personnel involved in the study will be blinded with regard to the IMP being administered with the exception of the pharmacist or designee at each site responsible for the preparation of subject doses who will not be blinded. A copy of the original randomisation code will be issued to the pharmacist or designee for this purpose.

The Bioanalytical Scientist (at Simbec) will be provided with a copy of the randomisation code for the purposes of analysing the samples. The Bioanalytical Scientist will provide the drug concentration data in a re-coded subject number format, in order to maintain the blind of study personnel. Re-coded PK data will also be included in an interim data report following completion of the single-dosing periods for each cohort. Analysis of the safety data will also be performed on blinded data.

Subject doses: Once the randomisation code has been authorised as per Simbec SOPs, each subject dose will be packaged and labelled for individual subjects by designated individuals from the Pharmacy Department at each clinical site on behalf of the Sponsor.

Code break envelopes: Once the randomisation code has been authorised as per applicable Simbec SOPs, the pharmacist or designee will produce individual sealed code-break envelopes that contain the treatment allocation(s) for each subject. The pharmacist or designee will provide the Principal Investigator with the applicable set of sealed envelopes. Each site will store the sealed envelopes in the restricted access pharmacy. A set of code break envelopes will also be provided to the person responsible for pharmacovigilance.

If the Investigator believes that knowledge of the IMPs received by a subject is essential for appropriate treatment of an AE, the Investigator should ideally consult the Sponsor before breaking the code. In any event, the Investigator should inform the Sponsor as soon as practical whenever the code has been broken for a subject. In the event that the site requires

GB-HV-01 Clinical Study Protocol Confidential RD 676/25641 Version: FINAL 6.0 / 05 April 2016 Page 45 of 73

emergency access to an individual subject code and personnel from the Sponsor are not available each site may break the blind without prior consultation with the Sponsor. In such an event, the Chief Investigator, Principal Investigator or delegate would notify the Sponsor as soon as possible *via* email or fax. If the Investigator needs to break the blind for an individual subject, the date and reason will be recorded in the subject's CRF. The Investigator will not reveal the unblinded treatment code to any other member of the clinical team involved in the study or to the Study Monitor. If the code is broken for any individual subject, the subject will be withdrawn from the study and the procedures accompanying withdrawal performed. If the code is broken without justification, this will be deemed a serious protocol violation.

9.6.10 Prior and Concomitant Therapy

Part 1: Prescribed drugs should not be taken for 14 days before the first dose and throughout the duration of the study-dosing period. Over the counter drugs and herbal remedies and supplements should not be taken from 14 days prior to the first dose and throughout the duration of the study dosing periods. Prescribed or over the counter drugs and herbal remedies and supplements taken during the 14 days before the first dose, and the reason for taking them, will be noted in the subject's CRF. Inclusion of subjects who have taken prescribed or over the counter medication during this period will be reviewed on a case-by-case basis in relation to the safety aspects and objectives of this study.

Part 2: Prescribed drugs should not be taken for 14 days before the first dose and throughout the duration of the study dosing period, with the exception of those listed in the study inclusion/exclusion section. Over the counter drugs and herbal remedies and supplements should not be taken from 14 days prior to the first dose and throughout the duration of the study dosing periods. Prescribed or over the counter drugs and herbal remedies and supplements taken during the 14 days before the first dose, and the reason for taking them, will be noted in the subject's CRF. Inclusion of subjects who have taken prescribed or over the counter medication during this period will be reviewed on a case-by-case basis in relation to the safety aspects and objectives of this study.

Concomitant medication should be avoided throughout the duration of the study dosing periods, with the exception of paracetamol (which may be taken as an analgesic to a maximum of 2 g in 24 hrs) and ibuprofen (which may be taken as an analgesic to a maximum of 1200 mg in 24 hrs [400 mg tds]), with the agreement of the Investigator.

If intake of concomitant medication becomes necessary for the treatment of an AE during the study, the daily dosage, duration and reasons for administration will be recorded on the subject's CRF. Subjects will inform the Investigator as soon as possible if concomitant medication was necessary during out-patient periods and the daily dosage, duration and reasons for administration will be recorded on the subject's CRF.

All concomitant medication taken during the screening period and between first dose and the Post-Study Visit will be recorded in the subject's CRF.

GB-HV-01 Clinical Study Protocol Confidential RD 676/25641 Version: FINAL 6.0 / 05 April 2016 Page 46 of 73

9.6.11 Treatment Compliance

When in the Clinical Unit, doses will be taken under supervision and the exact dosing time for each subject will be recorded on the subject's CRF. For doses administered by the subject at home, the dosing time will be recorded in a dosing diary.

9.7 Efficacy and Safety Variables

9.7.1 Efficacy and Safety Measurements Assessed and Flow Chart

Pre-study screening assessments will be carried out in the 28 day period before the first dose.

In **Part 1** post-study assessments will be carried out 12-16 days after the final study procedure on day 14.

In **Part 2** post-study assessments will be carried out 26 - 30 days after the last day of the Study Period.

All study personnel who have been appropriately trained will carry out study procedures.

The Study Flow Chart is provided in Table 9.7.1 and Table 9.7.2.

Where more than one procedure is scheduled for the same time-point, the following order of priority will apply:

- 1. PK and PD blood sampling (a window of \pm 2 min in relation to the nominal time-point is allowed)
- 2. Vital signs and 12-lead ECG (a window of \pm 10 min in relation to the nominal time-point is allowed. A window of \pm 30 mins will apply to the Day 14, 2h time point in Part 2 to fit around the BAL sampling procedure).

All pre-dose/baseline assessments may be performed within the 30 mins before dosing.

Confidential Page 47 of 73

Table 9.7.1 Part 1 Study Flow Chart

Visit	g .	Treatment Period							
	Screening		In-house			Post Study			
Day (h)	(Day -28 to -2)	Day -1	Day 1	Day 2 (24h)	Day 3 (48h)	Day 8 (168h)	Day 14 (312h)	(Day 26-30)	
Informed consent	X								
Inclusion/Exclusion	X	X							
Demographics	X								
Height / Weight / BMI ¹	X							X	
Medical History & Concurrent Conditions	X								
Biochemistry Haematology Urinalysis	X	X	X ²	X				X	
Virology	X								
Drugs of Abuse	X	X							
12-Lead ECG	X	X	X ³	X		X	X	X	
Physical Examination	X							X	
Vital Signs ⁴	X	X	X ⁵	X	X	X	X	X	
Spirometry (FEV1 & FVC)	X								
Dose			X						
PK Blood Sampling			\mathbf{X}^{6}	X	X				
PG & Flow Cytometry sampling		X	X ⁷	X				X	
Galectin-3 Blood sampling		X	X ⁸		X			X	
Exhaled Breath Condensate		X	X ⁹					X	
Adverse Events		+					·	—	
Concomitant Medication	X	4						—	

GB-HV-01 Clinical Study Protocol Confidential RD 676/25641 Version: FINAL 6.0 / 05 April 2016 Page 48 of 73

Table 9.7.1 Study Flow Chart Footnotes:

- 1. Height at Screening Visit only.
- 2. Laboratory safety samples will be taken at 6h post-dose.
- 3. 12-lead ECG to be measured prior to dosing = 0h and then at 30min and 2h post-dose.
- 4. Blood pressure, pulse, O₂ saturation, oral temperature, respiratory rate.
- 5. Vitals signs will be recorded prior to dosing = 0h and then at 5min, 15min, 30min, 2h, and 6h post-dose.
- 6. PK blood sampling will be taken prior to dosing = 0h and then at 15min, 30min, 45min, 1h, 2h, 3h, 4h, 5h, 6h, 12h and 18h post-dose.
- 7. Blood sampling for pharmacogenetic analysis (mRNA) and peripheral blood flow cytometry will be taken prior to dosing = 0h and then at 30min, 2h and 18h post-dose.
- 8. Blood sampling for Galectin-3 analysis will be taken prior to dosing = 0h and then at 5h post-dose.
- 9. Exhaled Breath Condensate will be taken prior to dosing = 0h and then at 1.5h post-dose.

Confidential Page 49 of 73

Table 9.7.2 Part 2 Study Flow Chart

Visit	Screening	Treatment Period						Post Study
Day	(Day -28 to -2)	Day -1	Day 1-3	Day 4-6	Day 7	Day 8-13	Day 14-15	(Day 41-45)
Clinic Visits	X	X	X		X		X	X
Informed consent	X							
Inclusion/Exclusion	X	X						
Demographics	X							
Height / Weight / BMI ¹	X							X
Medical History & Concurrent Conditions	X							
Biochemistry, Haematology, Urinalysis	X	X	X ²				X ²	X
Pregnancy Test	X							
Virology	X							
Drugs of Abuse	X	X						
12-Lead ECG	X	X			X^3		X^3	X
Physical Examination	X							X
Vital Signs ⁴	X	X	X ⁵		X^5		X ⁵	X
Spirometry ⁶	X						X ⁷	X
DLCO	X							
Dose ⁸			X	X	X	X	X	
PK Blood Sampling			X ⁹		X ⁹		X ⁹	
PG & Flow Cytometry Sampling			X ¹⁰		\mathbf{X}^{10}		X ¹⁰	
PBMC analysis			X ¹¹				X ¹¹	
Galectin-3 Blood sampling		X	X ¹²		X ¹¹		X ¹²	X
Exhaled Breath Condensate		X					X ¹³	X
Bronchoalveolar Lavage		X ¹⁴					X ¹⁴	
Adverse Events		•						
Concomitant Medication	X	◆						—

GB-HV-01 Clinical Study Protocol Confidential RD 676/25641 Version: FINAL 6.0 / 05 April 2016 Page 50 of 73

Table 9.7.2 Study Flow Chart Footnotes:

- 1. Height at Screening Visit only.
- 2. Laboratory safety samples will be taken on Day 1 at 6h post-dose, on Day 3 (prior to dosing) and Day 14 at 6h post-dose.
- 3. 12-lead ECG to be measured on Day 7 and Day 15.
- 4. Blood pressure, pulse, O₂ saturation, oral temperature, respiratory rate.
- 5. Vitals signs will be recorded on Day 1 prior to dosing = 0h and then at 5min, 15min, 30min, 2h, and 6h post-dose; Day 2, 3 and 7 prior to dosing = 0h; Day 14 prior to dosing = 0h and then at 5min, 15min, 30min, 2h, and 6h and 24h post-dose. (A window of ± 30 mins will apply to the Day 14, 2h timepoint in Part 2 to fit around the BAL sampling procedure)
- 6. Spirometry measurement to be recorded at equivalent time at each timepoint (\pm 1h).
- 7. Spirometry to be performed on Day 14 **prior** to BAL sampling procedure.
- 8. Subjects will be dosed with the IMP at the Clinical Centre during clinic visits and will self administer the IMP on non clinic visit days.
- 9. PK blood sampling will be taken on Day 1 prior to dosing = 0h and then at 15min, 30min, 45min, 1h, 2h, 3h, 4h, 5h, 6h and 12h post-dose; Day 2, 3 and 7 prior to dosing = 0h; Day 14 prior to dosing = 0h and then at 15min, 30min, 45min, 1h, 2h, 3h, 4h, 5h, 6h, 12h and 24h post-dose.
- 10. Blood sampling for pharmacogenetic analysis (mRNA) and peripheral blood flow cytometry will be taken Day 1 prior to dosing = 0h and then at 30 min post-dose, Day 7 at 2h post-dose and Day 14 prior to dosing = 0h and then at 30 min post-dose.
- 11. Blood sampling for pharmacogenetic analysis of peripheral blood mononuclear cells (PBMCs) will be taken Day 1 prior to dosing = 0h and Day 14 at 30 min post-dose.
- 12. Blood sampling for Galectin-3 analysis will be taken on Day 1 prior to dosing = 0h and then at 5h post-dose, Day 7 (anytime) and Day 14 prior to dosing = 0h.
- 13. Exhaled Breath Condensate to be performed on Day 14 between 1h and 2h post-dose.
- 14. BAL to be performed on Day 14 between 1h and 4h post-dose. (It is essential post treatment bronchoscopy is performed in the morning.)

GB-HV-01 Clinical Study Protocol Confidential RD 676/25641 Version: FINAL 6.0 / 05 April 2016 Page 51 of 73

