9.9 Statistical Methods and Determination of Sample Size

9.9.1 Statistical and Analytical Plan

9.9.1.1 Primary and Secondary Variables for Assessment

The primary safety assessment variables will be the vital signs data, ECG data, laboratory data and the adverse events reported.

The secondary pharmacokinetic variables will be the following non-compartmental pharmacokinetic end-points:

	Politica
• C _{max}	Maximum plasma concentration
• t _{max}	The time to maximum observed concentration sampled during
	a dosing interval
 λ_z 	Elimination rate constant
• t _{1/2}	Terminal half-life
• AUC _{0-t}	Area under the plasma concentration-time curve (AUC) from the
	time of dosing to the time of the last observed concentration
• AUC _{0-τ}	Area under the plasma concentration-time curve (AUC) from the
	time of dosing to time t at steady state
• AUC _{0-inf}	The area under the curve (AUC) extrapolated to infinity from dosing
	time, based on the last observed concentration
• CL/F	Plasma clearance, calculated as Dose / $AUC_{0\text{-}inf}$
AUC% extrapolated	Residual area

The secondary pharmacodynamic variables will be the peripheral blood flow cytometry data and galectin-3 plasma concentration data.

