The same analysis will be carried out (for C_{max} , AUC_{τ} , $t\frac{1}{2}$ and CL/F) for Part 2 of the study on Days 1, 7 and 14.

GB-HV-01 Clinical Study Protocol Confidential RD 676/25641 Version: FINAL 6.0 / 05 April 2016 Page 62 of 73

Accumulation Assessment: Log-transformed trough levels at pre-dose on Day 2 through to Day 14 will be used to establish any accumulation of TD139. The ratio of trough concentrations on each consecutive day will be presented and summarized along with a 90% confidence interval. The analysis will be done for each dose level.

Assessment of Steady State: Log-transformed trough concentration levels at pre-dose on Days 7, and 14 will be subjected to mixed effects ANOVA with study day as a fixed effect and subject as a random effect in order to establish whether and when steady state has been attained for each dose level. Back-transformed ratios for the Day 14/Day 7, comparisons will be presented along with corresponding 90% CI.

Additional PK Assessments:

Alveolar macrophage and BAL fluid concentrations of TD139 will be presented as a data listing.

Drug compartment measurements in BAL and alveolar macrophages will be analysed as per the method set out in the study by Naderer *et al*^[1] (e.g. TD139AM = TD139pellet/VAC [where the volume of alveolar cells - VAC, is estimated at 2.42μ l/106 cells])^[1].

PD Assessments:

Macrophage morphology parameters (*ex-vivo* macrophage function and BAL soluble markers) will be presented as a data listing.

Exhaled breath condensate data will be presented as a data listing.

Descriptive statistics of absolute and change from baseline for peripheral blood flow cytometry data will be presented at each time point by dose.

Descriptive statistics of absolute and change from baseline for Galectin-3 plasma concentration data will be presented at each time point by dose.

PG Assessments:

Macrophage phenotypic, mRNA pattern expression analysis from BAL and analysis of peripheral blood mononuclear cells for IPF gene signatures will be presented as a data listing.

Descriptive statistics of absolute and change from baseline of mRNA expression levels from blood leucocytes will be presented at each time point by dose.

Safety Assessments:

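### The Part 2 Day 7 galectin-3 sample has no fixed time relative to dose, so the Day 7 summary of this secondary PD variable may mix pre-dose and post-dose values

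*Protocol*

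**What the plan says.** Footnote 12 of Table 9.7.2 (Protocol, Section 9.7.1) sets the Part 2 galectin-3 times. Day 1 is tied to dose: "Blood sampling for Galectin-3 analysis will be taken on Day 1 prior to dosing = 0h and then at 5h post-dose". The same footnote continues: "Day 7 (anytime) and Day 14 prior to dosing = 0h". The flow chart adds samples on Day -1 and at the post-study visit.

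Day 7 is a clinic visit, and footnote 8 says: "Subjects will be dosed with the IMP at the Clinical Centre during clinic visits". The other Day 7 blood samples have fixed times. For PK, footnote 9 gives "Day 2, 3 and 7 prior to dosing = 0h". For mRNA and flow cytometry, footnote 10 gives "Day 7 at 2h post-dose and Day 14 prior to dosing = 0h".

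Section 9.9.1.1 gives the variable its status: "The secondary pharmacodynamic variables will be the peripheral blood flow cytometry data and galectin-3 plasma concentration data". Section 9.9.1.3 gives the planned summary: "Descriptive statistics of absolute and change from baseline for Galectin-3 plasma concentration data will be presented at each time point by dose".

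**The concern.** A table by time point assumes that each row holds values taken under the same conditions. For galectin-3 on Day 7, the only condition set is the calendar day. One subject may be sampled before the dose, at the end of the previous dosing interval, and the next some hours after it. Both comply, and both enter the same row.

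Day 7 is also the only galectin-3 sample between Day 1 and Day 14. Drawn pre-dose, it would line up with the 0h samples on those two days; drawn at 5h, it would line up with the Day 1 post-dose sample. The present wording secures neither. The protocol itself treats time from dose as worth fixing for this marker, since it samples at both 0h and 5h on Day 1.

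At stake is whether the Day 7 mean and change from baseline can be read as one quantity. Part 2 runs at four centres with 5 TD139 and 3 placebo subjects per initial cohort, so local habit could decide which phase is sampled, with few subjects to average it out.

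**Working it through.** The protocol states no figure to reproduce: it has no sample size calculation and gives no galectin-3 mean, SD or expected change. The check is first a comparison of the timing rules, then an illustration under stated assumptions.

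**Timing rules for Part 2 blood samples (Table 9.7.2, footnotes 9, 10 and 12)**

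| Sample | Day 1 | Day 7 | Day 14 |
|---|---|---|---|
| PK | 0h, then serial to 12h | 0h | 0h, then serial to 24h |
| mRNA and flow cytometry | 0h, 30 min | 2h | 0h, 30 min |
| Galectin-3 | 0h, 5h | no time set | 0h |

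The Day 7 visit therefore spans a pre-dose draw and a draw 2h after dose, so galectin-3 could practicably be taken in either phase. The tolerance in Section 9.7.1, "PK and PD blood sampling (a window of" 2 minutes either side of the nominal time), cannot act here because there is no nominal time. No other section limits the draw to one phase or says how mixed timings would be summarised. In the flow chart, the Day 7 galectin-3 cell is printed with marker 11, the PBMC note, which covers Days 1 and 14 only. Whether that is a slip or an artefact of text extraction, it supplies no Day 7 time.

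**Illustration of the effect on the Day 7 row**

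Inputs: n = 5 active subjects per initial cohort (Section 9.1). Assumption, not in the protocol: galectin-3 on active treatment differs by d between-subject SDs when drawn post-dose rather than pre-dose, with d from 0.25 to 1.0. Let k of the 5 be drawn post-dose, so p = k/5.

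- Shift of the Day 7 mean from its all-pre-dose value = p × d.
- SD factor = √(1 + p(1 − p)d²).

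| d (SD) | Mean shift, k = 1 (p = 0.2) | Mean shift, k = 4 (p = 0.8) | Largest SD factor (k = 2 or 3) |
|---|---|---|---|
| 0.25 | 0.05 | 0.20 | 1.007 |
| 0.5 | 0.10 | 0.40 | 1.030 |
| 1.0 | 0.20 | 0.80 | 1.114 |

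For the last cell: √(1 + 0.4 × 0.6 × 1²) = √1.24 = 1.114. If all 5 are drawn post-dose, the row is uniform but shifted by the full d from the pre-dose samples on Days 1 and 14. If d = 0, every entry is a zero shift and a factor of 1.

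**Drug level, for context only**

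Section 9.6.7 gives a non-clinical half-life of about 6h. If it held in patients, with simple first-order decay from the time of dosing, the fraction remaining is 2^(−t/6): 0.794 at 2h, 0.561 at 5h and 0.0625 at 24h. A 2h draw would then see 0.794/0.0625 = 12.7 times the 24h trough, and a 5h draw 0.561/0.0625 = 9.0 times. The limit is 1/0.0625 = 16 times. These ratios describe TD139, not galectin-3.

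**The case against.** The strongest reply is that little rests on this row. Section 9.9.2 calls all Part 2 PD measurements exploratory, and Section 9.9.1.3 plans only descriptive statistics for galectin-3, so no test or error rate is involved. Each cohort has concurrent, randomised, blinded placebo subjects. Section 9.7.5.2 has the actual draw time recorded, so values can later be sorted by time from dose. The open timing also looks deliberate, since neighbouring footnotes fix the other Day 7 draws. Mixing is permitted, not shown to happen.

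Most of this stands and keeps the point small. It does not remove it. Section 9.9.2 also says these data will inform a Phase 2b study, so readability matters. Sorting about 5 active subjects by phase would leave very few in each. A deliberate choice of open timing still leaves the row undefined relative to dose.

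Three stronger readings are tempting, and the protocol supports none of them:

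- A reader might infer that the galectin-3 course over Days 1, 7 and 14 cannot be interpreted. The contrast of Day 14 pre-dose with Day 1 pre-dose is untouched, as is the 0h to 5h contrast on Day 1.
- A reader might infer that a planned Day 7 versus Day 14 comparison is spoiled. No such galectin-3 comparison is planned. The only Day 14/Day 7 ratio in Section 9.9.1.3 is for trough drug concentrations, which are pre-dose on both days.
- A reader might take the 16-fold range as the size of the harm. It concerns drug level under a non-clinical half-life, and nothing in the protocol says plasma galectin-3 follows drug level within a dosing interval.

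**Conclusion.** The point holds in a narrow form, as a cheap improvement rather than a flaw that threatens a conclusion. The Day 7 galectin-3 row may pool pre-dose and post-dose values, and need not be like-for-like with the pre-dose samples on Days 1 and 14. The other galectin-3 rows are unaffected.

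The size cannot be fixed from the protocol, because the variation of galectin-3 within a dosing interval is not given. The illustrative range of 0.05 to 0.80 SD for the Day 7 mean, with SD inflation of at most about 11%, rests wholly on an assumed shift of 0.25 to 1.0 SD and on 1 to 4 of 5 active subjects being drawn post-dose. With no within-interval variation, the effect is nil.

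**What to change.** In footnote 12 of Table 9.7.2, replace the open Day 7 timing with a pre-dose (0h) sample, drawn with the existing Day 7 pre-dose PK sample and subject to the stated 2-minute PD sampling window. With one fixed time the mixing disappears by construction, and pre-dose is the choice that matches the Day 1 and Day 14 0h samples. Fixing 2h or 5h would also end the mixing, but would match Day 7 flow cytometry or the Day 1 post-dose sample instead.

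At the same time, check the marker on the Day 7 galectin-3 cell, printed as 11, and point it to footnote 12 if it is a slip.

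The change adds no visit, no venepuncture and no blood volume. Its cost is that sites lose flexibility on that one draw.

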9.7.1.1 Demographic and Background Assessments

Demographic and background assessments will be performed during the study at the time-points specified in the Study Flow Chart, Table 9.7.1 and Table 9.7.2 and include:

